Primary Hypothesis: Patients randomized to SCDM will demonstrate larger reductions in substance use measured by urine-confirmed self-reported days using over the 6-month follow-up compared to patients randomized to TAU.

Secondary Hypothesis (a): Patients randomized to SCDM will attend more specialty substance abuse intervention and treatment sessions over the 6 month follow-up than patients randomized to TAU.

Secondary Hypothesis (b): Patients randomized to SCDM will demonstrate a) reduced HIV transmission risk behaviors, and b) greater rates of HIV testing over the 6 month follow-up than patients randomized to TAU.

Exploratory Hypothesis: Patients randomized to SCDM will experience fewer days of rehospitalization and use of acute emergency services than patients randomized to TAU.

Aim 3: We will disseminate SCDM clinical techniques and the results of the clinical trial to the scientific community, the medical community, our stakeholders, and the public.

3. Endpoint(s) to be measured

Patient variables that will be measured include drug and alcohol use and problems, intervention and treatment engagement, health and medical functioning, hospital utilization (i.e. rehospitalization), psychosocial functioning, and HIV risk. In addition, client satisfaction, implementation barriers, and treatment integrity will be measured.

4. Number of subjects to be enrolled per year and in total. These numbers should incorporate numbers screened and consented to reach enrollment.

We anticipate screening approximately 1000 patients who are referred or flagged with a potential substance use issue, and have either a diagnosis of one of the targeted medical conditions or a previous hospitalization within the past six months. We expect approximately 25% of screened patients will

meet eligibility criteria and consent to take part in the study (about 250 patients). Of those patients consented, we expect approximately 222 participants will be enrolled to participate in the study (n=111 per condition).

Year 1: We anticipate we will screen and enroll 80 participants

Year 2: We anticipate we will screen and enroll 120 participants

Year 3: We anticipate we will screen and enroll 22 participants

Additionally, approximately 12 participants from the study will be enrolled into an additional sub-study in Year 1 and complete a semi-structured interview.

5. Considerations of statistical power in relation to enrollment

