Specialized Community Disease Management (SCDM): The SCDM intervention will last for 90 days and will be administered by a Licensed Clinical Social Worker (LCSW) functioning as a Behavioral Health Consultant (BHC) trained in evidence-based brief intervention and brief treatment approaches. After enrollment in the study, the BHC will conduct 1-2 brief intervention sessions at bedside. If a participant is discharged from the hospital before the BHC is able to conduct an initial brief intervention session, the BHC will contact the participant in the community and complete the initial session within one week after the participant's discharge from the hospital. These sessions will last 20-40 minutes each, and the BHC will employ motivational enhancement treatment (MET) with targeted behavioral strategies to create a problem-centered, flexible intervention strategy for patients at various levels of readiness to change. Patients are provided with direct normative feedback based on their use level and encouraged to quit or cut down. In most cases, this will include a discussion of the patient's past efforts to quit and previous treatment attempts. The BHC will negotiate an open, modifiable goal regarding how patients would like to handle their substance use. This approach is flexible as patients who would not consider treatment or working towards abstinence can often still connect with the BHC around less stringent goals (cutting down / harm reduction). The BHC's feedback will emphasize the importance of considering and engaging in treatment.

If a patient is willing to enter treatment, the BHC will work with the hospital discharge planning team to find suitable referrals and work to secure a place in an appropriate facility. Additionally, the BHCs will explore the participant's risk for contracting HIV and determine whether the patient has been tested; participants at risk who have not been tested recently will be encouraged to be tested while an inpatient. The BHC will provide the participant with various health communication materials from our Brief Intervention Toolkit. Finally, while still inpatient, the BHC will orient the participant to the procedures of the telephone-based follow-up calls and introduce the peer CHW, who can follow-up on treatment and recovery matters with participants (see below for the full description of the CHW's role).

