Temple University Hospital staff responsible for the patient's care (e.g., nurses, doctors, social workers) will be made aware that the patient is participating in the study so that hospital staff members do not duplicate treatment referral and case management efforts. After consent, the study social worker will insert a temporary chart flag into the patient's medical record indicating that the patient is enrolled in the study and which condition the patient is assigned to. This chart flag will be removed by hospital staff (which is standard procedure) after the patient is discharged from the hospital. During the consent process, patients will be informed that Temple staff responsible for their care will be notified that they are participating in the study and will also be notified which condition they are assigned to.

Participant Follow-up Procedures

We will complete follow-up assessment interviews with participants at 3 and 6 months after intake, as well as brief check-in calls at 1 and 2 months after intake. We will use patient-provided information on the Locator form to contact participants. If we are unable to contact the participant using Locator information, we will use contact information from the participant's TUH medical chart.

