Participant tracking software will be employed by the research staff to ensure that research staff are alerted when call windows open at each assessment point. Research staff will call participants at the times and numbers indicated on their Locator Form as the best time to reach them. For participants who are more difficult to reach, call times and call numbers will be alternated. Participants will also be mailed reminder notices informing them of an upcoming interview. Research staff will also attempt to contact participants via any other mechanisms that the participant consented to on the Locator (e.g. email, Facebook). For participants who are unreachable, messages will be left at all contacts that the participant consented to on the Locator Form. A postcard will also be mailed to the Locator contacts for whom the participant provided addresses to remind the participant of their upcoming appointment. Should contact persons indicate that they have lost track of the participant, research staff will search for the patient using available public search mechanisms (www.whitepages.com, etc.). If the participant still remains unreachable through all of the aforementioned methods, research staff will conduct an outreach visit to the home address that the participant provided on the Locator form. Research staff will travel in pairs when conducting home outreach and will not conduct outreach visits alone. When participants are reached, research staff will schedule the date and time of the interview, and will update the Locator Form in case the patient's contact information has changed.

Additionally, research coordinators may call a random selection of participants (up to 10%) who have completed follow-ups to 1) confirm that they completed a follow-up assessment with a research assistant, 2) confirm that they were compensated with the correct amount for the assessment, and 3) ask if they have any questions or concerns related to the study. To select participants for these check-in calls, we will randomly pre-assign each study ID number to be selected or not for the calls in an Excel spreadsheet separate from participant tracking. We will use a random number generator, and select the highest 10% of random numbers. These random checks will improve our data integrity and quality assurance procedures.

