Non-Study Medical and Other Services (NSMOS): This questionnaire was adapted from the Treatment Services Review (McLellan et al., 1992) for patients in medical settings. The NSMOS counts substance abuse treatment, medical services, visits to medical offices, hospitalizations, and emergency room visits received that were not a part of the assigned treatment. *Administered at 0,3,6 months. Brief version administered at 1 and 2 months.*

Temple Hospital Utilization Review: TUH conducts utilization reviews on all patients discharged for the targeted medical conditions to determine whether patients experience rehospitalization and use the emergency room. This data is pulled through a pre-written algorithm which can be adjusted to pull all inpatient and ER encounters over a six-month period. The TUH Institute for Population Health will supply this data for study participants.

HIV Risk Assessment (HIV-RA): The HIV Risk Assessment provides a brief self-report measure of HIV testing history and sexual risk and uses the preceding three months as the time interval of interest. The HIV-RA was developed [name], and [name], experts in the field of HIV risk behaviors. *Administered at 0,3,6 months.*

Addiction Severity Index-6th Edition Modified Version (ASI6-Modified). The ASI is a multi-dimensional interview used to measure the substance use, health, and social problems of those with alcohol and other drug problems, both at admission to treatment and subsequently at follow-up contacts (McLellan et al., 1992; McLellan et al., 1980). We are using an abbreviated version of the ASI-6 that eliminates many of the items that do not contribute to our primary hypotheses and takes approximately 20 minutes to complete. We will use only the ASI domains for medical, drug use, alcohol use, and psychological status for covariate analysis. The ASI-6 produces Recent Status Scores in each of these four areas, which have demonstrated high levels of inter-rater, test-retest, and concurrent reliability (Cacciola et al., 2011). *Administered at 0,3,6 months.*

Healthy Days Symptoms: The Healthy Days Symptoms Module (Newschaffer, 1998) was taken from the CDC's Health-Related Quality of Life Survey, which is part of the State-based Behavioral Risk Factor Surveillance System (BRFSS). This module measures the number of days over the past month that a patient was affected by symptoms such as pain and anxiety, as well as the number of healthy days. *Administered at 0,3,6 months.*

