SAS's PROC MIXED. Should the rate of disagreement between urine and self-report exceed acceptable standards; we will analyze the urine results as the primary outcome. However, the literature indicates that self-report of substance use is generally quite accurate ^{4,5}.

Secondary hypothesis (a): Patients assigned to the SCDM condition will exhibit greater reductions in days of hospitalization and acute emergency care over the six-month period than patients assigned to TAU. A linear mixed effects model ² will be used to compare participants in the two groups on the days of inpatient and ED utilization in the past 90 days at the 3 and 6-month follow-up assessments. The model will be similar to that outlined for the primary hypothesis.

Secondary hypothesis (b): Patients assigned to the SCDM condition will demonstrate higher rates of engagement in substance abuse treatment than patients assigned to TAU. A linear mixed effects model ² will be used to compare patients in the two groups on the number of treatment sessions attended in the past 90 days at the 3 and 6-month assessments, similar to that outlined for the primary hypothesis.

Exploratory hypothesis: Patients randomized to SCDM will demonstrate a) reduced HIV transmission risk behaviors, and b) greater incidence of HIV testing over the 6 month follow-up than patients randomized to TAU. Secondary efficacy analyses will be conducted to examine the effects of the intervention on HIV related behaviors. A linear mixed effects model ² will be used to compare the two groups' RAB scores (i.e., total, sex, drug) at months 3 and 6. The baseline response will be included as a covariate. A logistic regression model will be employed to test differences in incidences of testing.

References:

1. Tabachnik B, & Fidell, L.S. *Using multivariate statistics*. Boston, Massachusetts: Allyn and Bacon; 1994.

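### The three-month look-back for HIV testing leaves no margin for a late or missed month-3 interview, so tests near intake can fall outside the six-month endpoint

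*Protocol*

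**What the plan says.** Protocol item 7 describes the HIV-RA as a "brief self-report measure of HIV testing history and sexual risk" that "uses the preceding three months as the time interval of interest", given at 0, 3 and 6 months. The wording of the testing item is not shown.

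Protocol item 6, Participant Follow-up Procedures, sets the schedule: "We will complete follow-up assessment interviews with participants at 3 and 6 months after intake". It says that "research staff are alerted when call windows open at each assessment point", but gives no width and no latest date. The brief calls at months 1 and 2 cover hospitalizations, emergency visits and substance use, not HIV testing.

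In the SCDM arm (item 6), the Behavioral Health Consultant holds bedside sessions after enrollment and explores HIV risk; "participants at risk who have not been tested recently will be encouraged to be tested while an inpatient". The TAU arm gets one session from the same consultant. It is called similar to the SCDM strategy, but its listed contents are normative feedback, encouragement towards substance use treatment, and referral.

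Secondary Hypothesis (b) in Protocol item 2 predicts "greater rates of HIV testing over the 6 month follow-up" with SCDM. The SAP ranks the HIV outcomes as exploratory and says only: "A logistic regression model will be employed to test differences in incidences of testing". It names no item, visits or recall period for that outcome. The chart data listed in Protocol item 13 do not include HIV tests.

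**The concern.** The recall period and the visit interval have the same length, so there is no overlap to absorb a visit that slips. The part of follow-up that drops out first is the days just after intake. Those are the days when SCDM, as described, encourages an inpatient test. The baseline HIV-RA will usually have been completed before that test, and the month-6 look-back reaches back only to about month 3. A test lost at month 3 is therefore counted nowhere.

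At stake is whether the testing outcome measures what the hypothesis states, namely testing over six months. If one arm has more tests in the uncovered days, the comparison is distorted as well as less complete.

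**Working it through.** **The plan's own figure.** The only power statement (Protocol item 5; SAP, Power Analysis) concerns the primary outcome: two-sided alpha 0.05, d = 0.4, intraclass correlation 0.7, 15% attrition, 111 per arm, 85% power. With two follow-ups the variance factor is (1 + 0.7)/2 = 0.85 and n = 111 × 0.85 = 94.35 per arm. Then z = 0.4/√(2 × 0.85/94.35) − 1.96 = 2.98 − 1.96 = 1.02, a power of 84.6%. The stated figure reproduces, and nothing below affects it. The documents give no power, testing rate or lateness figure for HIV testing.

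**Coverage.** Count days from intake and take three months as 90 days. A month-3 interview held on day 90 + L looks back to day L. A test on day t is missed when L > t. An interview on time or early (L ≤ 0) loses no test done on or after intake. If the interview does not take place, the look-back of an on-time month-6 interview starts at day 90 and days 0-90 are uncovered.

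**How often L > t.** This needs assumptions. With L and t uniform over whole days and independent:

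| Assumed L (days) | Assumed t (days) | Inpatient tests missed | Late visits that still capture the test |
|---|---|---|---|
| −7 to +7 | 1 to 7 | 21/105 = 20% | 28/49 = 57% |
| 0 to +30 | 1 to 7 | 26/31 = 84% | 4/30 = 13% |

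Over all the windows tried (−7 to +7, 0 to +14, −14 to +30, 0 to +30) and test days (0-3, 1-7, 1-14), the share missed runs from 10% to 92%. A range that wide shows that the documents do not fix the size.

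**Effect on the comparison.** Let b be other testing, equal in both arms and fully captured; qS and qT the shares tested as inpatients in SCDM and TAU; and f the share of inpatient tests missed, equal in both arms. The observed rate in an arm is 1 − (1 − b)(1 − q(1 − f)), so

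observed difference = (1 − b)(1 − f)(qS − qT).

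The difference shrinks by the factor (1 − f). If qS = qT it is zero at every f, and this mechanism adds no bias.

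Power below is for a two-sided two-proportion test at 0.05 with 94 per arm: Φ{(|pS − pT| − 1.96√[2p̄(1 − p̄)/94]) / √[(pS(1 − pS) + pT(1 − pT))/94]}. All rates are assumed: b = 10%, qS = 20%, qT = 0.

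| f | SCDM | TAU | Difference (points) | Odds ratio | Power |
|---|---|---|---|---|---|
| 0 | 28.0% | 10% | 18.0 | 3.50 | 89% |
| 0.25 | 23.5% | 10% | 13.5 | 2.76 | 70% |
| 0.50 | 19.0% | 10% | 9.0 | 2.11 | 42% |
| 0.75 | 14.5% | 10% | 4.5 | 1.53 | 15% |

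With some inpatient testing in TAU (b = 10%, qS = 30%, qT = 10%), the difference is again 18.0 points at f = 0 and 9.0 at f = 0.5, and power falls from 79% to 35%.

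**The case against.** **The instrument is not shown.** A testing-history item could be dated or have longer recall, with the three-month interval meant for the risk items. This cannot be ruled out. Still, the protocol states the interval for the instrument as a whole, and neither document describes an exception.

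**Any late visit loses the inpatient test.** A reader might infer this, but it is wrong. The visit must be later than the number of days from intake to the test. Under the ±7-day assumption above, more than half of late visits still capture it.

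**The comparison is biased towards no effect.** A reader might infer this too, but the documents do not establish it. It requires more inpatient testing in SCDM than in TAU. The TAU session is called similar and comes from the same consultant; HIV testing is not listed for it, which leaves the contrast probable but not certain. It also requires a similar loss in both arms. If lateness differed by arm, the distortion could go either way.

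**Inpatient tests may not be the whole effect.** SCDM continues with 12 weeks of calls aimed partly at reducing risk, and with peer visits. Tests prompted later are less exposed to the loss. If half of the assumed 20% came later and were captured, then at f = 0.5 the difference would be 0.9 × (0.10 × 0.5 + 0.10) = 13.5 points, not 9.0.

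**Lateness is not documented.** The reminders, locator updates and outreach are there to keep visits on time. They also show that the trial expects participants who are hard to reach, and no closing date for a visit is given.

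**Conclusion.** The point holds as a weakness of coverage. Followed as written, a three-month look-back at visits three months apart does not guarantee that the six-month testing endpoint is observed. Tests soon after intake are lost when the month-3 interview is late by more than the days from intake to the test, or is missed. Neither the month-1 and month-2 calls nor the listed chart data recover them.

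The pull towards no effect is conditional: it needs commoner inpatient testing in SCDM and a similar loss by arm. On those conditions the difference shrinks in proportion to the share of inpatient tests missed. That share ranged from 10% to 92% under the lateness and test-day patterns tried, so no single magnitude can be claimed for this trial.

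A reader might also infer that the trial's power is impaired. It is not: the stated 85% belongs to the primary substance-use outcome. This is an inexpensive improvement to an endpoint that is secondary in the protocol and exploratory in the SAP.

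**What to change.** For the HIV-testing item only, ask at month 3 about testing *since the baseline interview (date)* and at month 6 about testing *since the last completed interview (date)*, and record the date of each test. The second wording also covers a missed month-3 interview. Keep the three-month interval for the risk-behaviour items.

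In the SAP, define the outcome as any HIV test dated after randomization and within six months of it, and name the item and visits that supply it. State the visit window in the protocol. The SAP names RAB scores with a drug subscale where the protocol names the HIV-RA, so the instrument should be reconciled in the same edit.

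The cost is one reworded item, a date field and a sentence or two in the SAP. Recall becomes somewhat longer for participants seen late or after a missed visit. Timing is the larger limit. The protocol is dated March 2016, at the start of the third funding year, and 80 + 120 = 200 of the 222 enrolments were planned for the first two years. A change made mid-trial mixes two recall periods, which the analysis must note. For interviews already held under the three-month wording, the report should use the interview dates to show by arm how many participants had uncovered days after intake.

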Study Title: Specialized Community Disease Management to Reduce Substance Use and Hospital Readmissions

NCT Number: NCT02059005

Document Date: June 30, 2017

Data Analysis Plan

Analyses will compare outcomes for the TAU and SCDM groups. We will employ remedial measures such as power transformations when necessary. We will confirm that the groups do not differ at baseline on relevant background variables using t-tests for continuous variables and chi-square tests for discrete or ordinal responses. The randomization process should minimize the need for the inclusion of covariates to reduce bias in the treatment comparisons ¹. However, relevant covariates will be considered for inclusion in the analyses to improve the precision of estimation of the effects ².

Power Analysis. The power analysis for the primary hypothesis was conducted following the recommendations of Diggle et al. ³ for mixed effects models. Using a two-sided alpha of .05, an estimated intraclass correlation of .7 between the repeated measurements, and a 15% attrition rate by month 6, we will have 85% power to detect a moderate effect of the intervention ($d = .4$) with a sample size of 111 patients in each group (222 altogether).

Primary hypothesis: Patients assigned to the SCDM condition will report significantly fewer days of substance use than patients assigned to TAU. Using TLFB data, we will create a variable for days of any substance use by combining all drug types and alcohol. Urine samples collected at months 3 and 6 will be used to confirm reports of drug use. Provided that the rate of disagreement between urine results and self-report is acceptable (below 15%), we will analyze days of substance use as a unitary variable. A linear mixed effects model ² will be used to examine days of self-reported drug use in the past 30 days at each follow-up assessment. Mixed effects models have advantages over conventional repeated measures methods in that they allow for missing observations, accommodate measurements made at different time points, provide greater flexibility in modeling the variance-covariance matrix, and permit the estimation of group and random subject-specific effects. The model will include terms for condition, assessment point, and their interaction along with any necessary covariates including the number of days of use reported at the baseline. The analysis will be conducted using

SAS's PROC MIXED. Should the rate of disagreement between urine and self-report exceed acceptable standards; we will analyze the urine results as the primary outcome. However, the literature indicates that self-report of substance use is generally quite accurate ^{4,5}.

Secondary hypothesis (a): Patients assigned to the SCDM condition will exhibit greater reductions in days of hospitalization and acute emergency care over the six-month period than patients assigned to TAU. A linear mixed effects model ² will be used to compare participants in the two groups on the days of inpatient and ED utilization in the past 90 days at the 3 and 6-month follow-up assessments. The model will be similar to that outlined for the primary hypothesis.

Secondary hypothesis (b): Patients assigned to the SCDM condition will demonstrate higher rates of engagement in substance abuse treatment than patients assigned to TAU. A linear mixed effects model ² will be used to compare patients in the two groups on the number of treatment sessions attended in the past 90 days at the 3 and 6-month assessments, similar to that outlined for the primary hypothesis.

Exploratory hypothesis: Patients randomized to SCDM will demonstrate a) reduced HIV transmission risk behaviors, and b) greater incidence of HIV testing over the 6 month follow-up than patients randomized to TAU. Secondary efficacy analyses will be conducted to examine the effects of the intervention on HIV related behaviors. A linear mixed effects model ² will be used to compare the two groups' RAB scores (i.e., total, sex, drug) at months 3 and 6. The baseline response will be included as a covariate. A logistic regression model will be employed to test differences in incidences of testing.

References:

1. Tabachnik B, & Fidell, L.S. *Using multivariate statistics*. Boston, Massachusetts: Allyn and Bacon; 1994.

